9.1.7 Data Monitoring Committee

A data monitoring committee (DMC) will be formed. The DMC objectives and operational details will be defined in a separate document (DMC Charter), which will be finalized before the first subject is screened. The DMC will conduct regular planned reviews of study data as outlined in the DMC Charter.

9.2 Method of Assigning Subjects to Treatment Groups

Subjects will be randomized (1:1) to the ELX/TEZ/IVA or placebo group. Randomization will be stratified by LCI_{2.5} determined at the Screening Visit (<10 versus ≥10) and weight at the Screening Visit (<30 kg versus ≥30 kg).

An interactive web response system (IWRS) will be used to assign subjects to treatment. The randomization code will be produced by Vertex Biostatistics or a qualified randomization vendor. The Vertex study biostatistician will review and approve the production of the final randomization list, which will be reviewed and approved by a designated unblinded biostatistician who is not a member of the study execution team (SET).

9.3 Rationale for Study Elements

9.3.1 Study Design

A randomized, double-blind, placebo-controlled study design was selected to ascertain the effects of ELX/TEZ/IVA through between-group comparisons while avoiding observer bias. Placebo is considered the appropriate comparator because no CFTR modulator regimen has been approved for use in subjects 6 through 11 years of age who have F/MF genotypes.

The rationale for including absolute change in LCI_{2.5} from baseline through Week 24 as the primary endpoint is discussed in Section 9.3.4.

9.3.2 Study Population

This study will enroll CF subjects with F/MF genotypes, 6 through 11 years of age. ELX/TEZ/IVA is expected to provide clinical benefit to these patients based on the results of a Phase 3 study (Study VX17-445-102), which demonstrated the efficacy and safety of ELX/TEZ/IVA in CF subjects ≥12 years of age who have F/MF genotypes.

Given the progressive nature of CF, there is a strong rationale for treating patients earlier in life. Experience with CFTR modulators, including TEZ/IVA, in pediatric subjects 6 to 11 years of age, suggests that the safety profile of ELX/TEZ/IVA will be similar in children and adults, which supports evaluation of ELX/TEZ/IVA in pediatric subjects in the present study.

9.3.3 Study Drug Dose and Duration

Study Drug Dose

The dose of ELX/TEZ/IVA evaluated in the pivotal Phase 3 study in subjects with F/MF genotypes ≥12 years of age (200 mg qd/100 mg qd/150 mg q12h) was generally safe and well tolerated and resulted in clinically meaningful improvements compared to placebo in endpoints including ppFEV₁ (LS mean treatment difference of 14.3 percentage points [p<0.0001] for

absolute change from baseline) and SwCl (LS mean treatment difference of -41.8 mmol/L [$p < 0.0001$] for absolute change from baseline) through 24 weeks.

The doses of ELX/TEZ/IVA administered in this study (200 mg qd/100 mg qd/150 mg q12h for subjects ≥ 30 kg, 100 mg qd/50 mg qd/75 mg q12h for subjects < 30 kg) have been selected through assessment of PK over approximately 2 weeks in Part A of a registrational Phase 3 study in 6 to 11 year of age CF subjects, and are the same doses being administered over 24 weeks in Part B of that registrational study.

Treatment Duration

This study will have a 24-week treatment duration to allow for placebo-controlled assessment of safety and efficacy over 24 weeks of treatment.

9.3.4 Rationale for Study Assessments

Most of the safety, efficacy, and PD assessments are standard parameters for clinical studies in drug development and are generally recognized as reliable, accurate, and relevant to the study of subjects with CF. Baseline and follow-up ophthalmologic examinations are recommended for monitoring of pediatric patients treated with IVA-containing drug regimens, and have been added to the standard safety assessments.

LCI is a measure of ventilation inhomogeneity assessed by multiple-breath washout (MBW) that is based on tidal breathing techniques that have been evaluated in patients as young as infants.^{14, 15} Studies have shown that LCI correlates with FEV₁ in its ability to measure airway disease and can detect lung disease at an earlier stage than spirometry.^{16, 17}

9.4 Study Restrictions

9.4.1 Prohibited Medications

Table 9-2 lists prohibited medications. A non-exhaustive list of study prohibitions and cautions for medication will be provided in the Study Reference Manual.

Table 9-2 Prohibited Medications

Medication	Timing of Restriction		Rationale
	Start of Restriction	End of Restriction	
Moderate and strong CYP3A inducers	None allowed within 14 days before the first dose of the study drug on Day 1	None allowed through completion of study participation	ELX, TEZ, and IVA are metabolized extensively via CYP3A4. Therefore, use of moderate and strong inducers and inhibitors of CYP3A, which have the potential to alter the exposure of ELX, TEZ, or IVA, will be prohibited.
Moderate and strong CYP3A inhibitors (except ciprofloxacin) ^a	None allowed within 14 days before the first dose of the study drug on Day 1	None allowed through completion of study participation	
CFTR modulators (investigational or approved), except for study drugs	None allowed within 28 days before the first dose of the study drug on Day 1	None allowed until after the last dose of study drug	These agents may confound the results of this study.

Table 9-2 Prohibited Medications

Medication	Timing of Restriction		Rationale
	Start of Restriction	End of Restriction	

CYP: cytochrome P450; ELX: elxacaftor; IVA: ivacaftor; TEZ: tezacaftor

^a Ciprofloxacin is not a moderate CYP3A inhibitor on the basis of results of a drug-drug interaction study conducted with IVA, a sensitive CYP3A substrate (Kalydeco [ivacaftor] US Package Insert).

9.5 Prior and Concomitant Medications

Information regarding prior and concomitant medications, including CF medications, other medications, and herbal and naturopathic remedies, will be collected from each subject's source documentation for medications taken within 56 days before the Screening Visit through completion of study participation, as defined in Section 9.1.6.

For subjects who are screened but are not subsequently enrolled, details of prior medication will be documented only in the subjects' source documents.

- Subjects should remain on a stable treatment regimen for their CF from 28 days before the Day 1 Visit through completion of study participation. Stable treatment regimen is defined as the current treatment regimen for CF that subjects have been following for at least 28 days before the Day 1 Visit. Subjects should not initiate long-term treatment with new medication from 28 days before the Day 1 Visit through completion of study participation. Guidelines for stable treatment regimens for CF are as follows:
 - o Subjects who are taking inhaled tobramycin or other chronically inhaled antibiotics should remain on that regimen throughout the study.
 - o Subjects who cycle onto and off of an inhaled antibiotic should continue on their prior schedule. The timing of the first dose of study drug on the Day 1 Visit should be synchronized as closely as possible (e.g., not more than ± 3 days) to the first day in the cycle onto the inhaled antibiotic.
 - o Subjects who alternate between 2 different inhaled antibiotics should remain on the same cycling schedule during the study. The timing of the first dose of study drug on the Day 1 Visit should be synchronized as closely as possible (e.g., not more than ± 3 days) to the first day in the cycle onto 1 of the inhaled antibiotics.
- Subjects may receive doses of prednisone or prednisolone of up to 10 mg/day chronically, or up to 60 mg daily for up to 5 days.
- ELX may inhibit OATP1B1 and OATP1B3, which may increase the exposure of medicinal products that are substrates for these transporters. Substrates such as statins, glyburide, nateglinide, and repaglinide should be used with caution.
- IVA is a weak inhibitor of P-glycoprotein (P-gp). Administration of IVA may increase systemic exposure of medicinal products that are sensitive substrates of P-gp, which may increase or prolong their therapeutic effect and adverse reactions. Digoxin or other substrates of P-gp with a narrow therapeutic index, such as cyclosporine, everolimus, sirolimus, and tacrolimus, should be used with caution and appropriate monitoring.

- IVA may inhibit CYP2C9; therefore, during coadministration with warfarin, additional monitoring of the international normalized ratio is recommended. Other medicinal products that are CYP2C9 substrates for which exposure may be increased include glimepiride and glipizide; these should be used with caution.
- Information about bronchodilator use during the study will be collected and documented. Subjects who are using a bronchodilator should have their spirometry assessments performed according to the guidelines provided in Section 11.3.2.

9.6 Administration

9.6.1 Dosing

Study drug tablets will be administered orally as shown in Table 9-3. Subjects in both treatment groups (ELX/TEZ/IVA and placebo) will receive the same number of tablets each day to maintain the blind. Additional information is provided in the Pharmacy Manual.

Table 9-3 Study Drug Administration

Subject Weight at Screening	Tablet Strength	Time	Number of Tablets Taken
<30 kg	50-mg ELX/25-mg TEZ/37.5-mg IVA	AM	2 tablets
	75-mg IVA	PM	1 tablet
≥30 kg	100-mg ELX/50-mg TEZ/75-mg IVA	AM	2 tablets
	150-mg IVA	PM	1 tablet

ELX: elexacaftor; IVA: ivacaftor; TEZ: tezacaftor

Study drug should be administered with a fat-containing meal or snack, such as a standard “CF” meal or snack or a standard meal according to the following guidelines:

1. It is recommended that the dose be taken within approximately 30 minutes of the start of the meal or snack.
2. All doses of study drug (morning and evening, as applicable) should be administered at approximately every 12 hours (\pm 2 hours) on each dosing occasion (e.g., if the morning doses of study drug are administered at 08:00 hour on Day 1, all subsequent morning doses should be administered between 06:00 hour and 10:00 hour).
3. At the Day 1 Visit, all subjects will be observed for 4 hours after the morning dose of the study drug.
4. On days of scheduled visits, the morning dose of study drug will be administered at the site after predose assessments have been completed. The meal or snack will be provided by the site for the morning dose of study drug.
5. For visits after the Day 1 Visit, subjects will be instructed to bring all used and unused study drug to the site; study drug will be dispensed at each visit, as appropriate.
6. At the Week 24 Visit, the morning dose of study drug will NOT be administered. The last dose of study drug will be the evening dose administered the day before the Week 24 Visit.

9.6.2 Missed Doses

If 6 hours or less have passed since the missed morning or evening dose, the patient should take the missed dose as soon as possible and continue on the original schedule.

Morning dose: If more than 6 hours have passed since the missed **morning** dose, the patient should take the missed dose as soon as possible and should not take the evening dose.

Evening dose: If more than 6 hours have passed since the missed **evening** dose, the patient should not take the missed dose. The next scheduled morning dose should be taken at the usual time.

Morning and evening doses should not be taken at the same time.

9.7 Dose Modification for Toxicity

Modifications of the study drug dose are prohibited. Should any unacceptable toxicity arise, individual subjects will be withdrawn from the study and dosing will cease.

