9.1.2 Treatment Period

The Treatment Period will last approximately 24 weeks. Study drug administration details are provided in Section 9.6.

Subjects who prematurely discontinue study drug treatment will remain in the study from the time of discontinuation of study drug treatment through the last scheduled study visit and complete the assessments for all study visits, as described in Section 9.1.4.

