9.1.4 Early Termination of Treatment

If a subject prematurely discontinues study drug treatment, an Early Termination of Treatment (ETT) Visit should be scheduled as soon as possible after the decision to discontinue treatment. Subjects who prematurely discontinue treatment will also be required to complete the Safety Follow-up Visit (Table 3-2) if applicable (Section 9.1.3).

If a subject withdraws from the study and also withdraws consent or assent, no further assessments will be performed. Vertex may retain and continue to use any data and samples collected before such withdrawal of consent or assent.

If the ETT Visit occurs 3 weeks or later following the last dose of study drug, then the ETT Visit will replace the Safety Follow-up Visit, and a separate Safety Follow-up Visit will not be required.

Subjects who prematurely discontinue study drug treatment will continue to complete all scheduled study visits for assessments following completion of the ETT Visit, as detailed in Table 3-2.

Subjects who prematurely discontinue treatment are not eligible to enroll in the optional open-label extension safety study.

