9.8.1 Liver Function Tests

The central laboratory will notify the medical monitor of ALT or AST $>3 \times \text{ULN}$ and total bilirubin $>2 \times \text{ULN}$ that are derived from centrally submitted samples.

Subjects with new treatment-emergent ALT or AST elevations of $>3 \times \text{ULN}$, with or without total bilirubin $>2 \times \text{ULN}$, must be followed closely, including confirmatory testing performed by the central laboratory within 48 to 72 hours of the initial finding and subsequent close monitoring of ALT, AST, and bilirubin levels, as clinically indicated.

If a subject cannot return to the site for confirmatory testing, a local laboratory may be used. Local laboratory results must be reported immediately to the medical monitor, and the subject must have the tests repeated and sent to the central laboratory as soon as possible (ideally within 48 to 72 hours).

Study drug administration **must be interrupted** immediately (prior to confirmatory testing) if any of the following criteria are met:

- ALT or AST $>8 \times \text{ULN}$
- ALT or AST $>5 \times \text{ULN}$ for more than 2 weeks

- ALT or AST $>3 \times$ ULN, in association with total bilirubin $>2 \times$ ULN and/or clinical jaundice

A thorough investigation of potential causes should be conducted, and the subject should be followed closely for clinical progression.

Study drug administration **must be discontinued** if the following criterion is met:

- Subsequent ALT or AST values confirm the initial elevation that satisfied the interruption rule (above), and no convincing alternative etiology (e.g., acetaminophen use, viral hepatitis, alcohol ingestion) is identified, regardless of whether transaminase levels have improved.

All subjects in whom treatment is discontinued for elevated transaminases (and bilirubin, as applicable) should have these levels monitored closely until levels normalize or return to baseline.

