9.8.2 Rash

Individuals who develop a generalized rash will be monitored closely. Study drug dosing should be interrupted if a subject develops a generalized rash of Grade 3 or higher (Section 13.1.1.4), or a rash that is considered a serious adverse event (SAE). The investigator will notify the medical monitor of any rash that results in interruption of study drug, is Grade 3 or higher, or is an SAE. Investigators should consider additional evaluation including laboratory testing (e.g., complete blood count with differential, liver function tests), photographs of the rash, and dermatology consultation. The investigator may consider resumption of study drug if considered clinically appropriate.

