9.9 Removal of Subjects

Subjects may withdraw from the study at any time at the request of the subject's parent or legal guardian. Subjects may be withdrawn from study drug treatment at any time at the discretion of the investigator or Vertex for safety, behavior, noncompliance with study procedures, or administrative reasons. If a subject has been withdrawn from study drug treatment, the subject will continue to be followed, provided that the subject has not withdrawn consent (and assent, as applicable).

In addition, a subject must be discontinued from study drug treatment if the subject meets any of the following criteria:

- Has a screening CFTR genotype that does not confirm study eligibility if a previous CFTR genotype laboratory report was used to establish eligibility. These subjects must be discontinued from the study (Section 8.1)
- Meets any of the stopping (discontinuation) criteria (Section 9.8)

- Becomes pregnant (Section 11.5.6.2)

Subjects who discontinue study drug treatment should return for study assessments, as noted in Section 9.1.4.

If a subject does not return for a scheduled visit, reasonable effort will be made to contact the subject. In any circumstance, reasonable effort will be made to document subject outcome. The investigator will inquire about the reason for withdrawal, request that the subject return all unused investigational product(s), request that the subject return for an ETT Visit and Safety Follow-up Visit, if applicable (see Section 9.1.4), and follow up with the subject regarding any unresolved AEs.

If the subject withdraws consent or assent for the study, no further assessments will be performed. Vertex may retain and continue using the study data and samples after the study ends, and may use the samples and information in the development of the study compounds, and for other drugs and diagnostics, in publications and presentations, and for education purposes. If the subject withdraws from the study, the study data and samples collected will remain part of the study. A subject will not be able to request the withdrawal of his or her information from the study data. A subject may request destruction of the samples collected from him/her during the study as long as those samples can be identified as his or her samples.

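### Protocol 9.7 withdraws children with any unacceptable toxicity from the study, while 9.1.2, 9.1.4, 9.1.6 and 9.9 keep them in scheduled visits; the likely effect on the primary result is small

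*Protocol*

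**What the plan says.** Protocol 9.7 forbids any change of dose and then covers unacceptable toxicity of any kind: "individual subjects will be withdrawn from the study and dosing will cease". That states two consequences, leaving the study and stopping drug.

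Four other sections give a different outcome for a child who stops drug early:

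- **9.1.2:** "Subjects who prematurely discontinue study drug treatment will remain in the study from the time of discontinuation", with assessments up to the last scheduled visit.
- **9.1.4:** these subjects "will continue to complete all scheduled study visits for assessments following completion of the ETT Visit".
- **9.1.6:** for a child who stops drug but keeps consent, participation ends at the latest of the Week 24, ETT or (if required) Safety Follow-up Visit. No category describes an exit for toxicity.
- **9.9:** safety is listed as a ground for stopping study drug. It adds: "If a subject has been withdrawn from study drug treatment, the subject will continue to be followed", provided consent (and assent) stands.

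On the analysis side, SAP 9.3.1.2 fits the mixed model to LCI2.5 change at Day 15 and Weeks 4, 8, 16 and 24, averages the last four, and assumes missing at random. SAP 9.3.2.2 does the same for sweat chloride. SAP Appendix A assigns values to windows by study day and keeps one value per window. The public text has no rule that drops values measured after drug is stopped.

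**The concern.** The same event, stopping drug for toxicity, ends participation under one section and continues it under four others. The literal reading of 9.7 is not fanciful. Section 9.9 uses the same idea as a true exit for children whose genotype is not confirmed: "These subjects must be discontinued from the study (Section 8.1"). In the same section, safety cases leave only study drug treatment.

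If a site takes 9.7 at its word, the child's scheduled visits after the ETT Visit do not happen. Table 3-2 schedules washout and sweat chloride at the ETT Visit but not at Safety Follow-up, so the latter cannot replace them. Later scheduled safety assessments go too, although the safety tables reach only 28 days past the last dose in any case. The missing LCI2.5 values would come from children who have lost the drug's benefit. Under missing at random, the model predicts those values largely from children still on drug, which pushes the estimated difference in the drug's favour.

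**Working it through.** **1. The plan's own figures.** Inputs from Protocol 12.1: difference 1.0, SD 1.5, two-sided alpha 0.05, 49 completers per group, 10% dropout.

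- Two-sample t-test power (noncentral t) with 49 per group is 90.4%, and 49 is the smallest group size that reaches 90%. This matches the stated figure of about 90%.
- 98/0.9 = 108.9, against about 108 stated.
- Planned standard error = 1.5 × √(2/49) = 0.303.
- Rewording 9.7 changes none of these. As a bound, losing 1, 3 or 5 further active-arm children beyond the planned dropout takes power to 90.1%, 89.5% or 88.8%.

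**2. Visits lost per exiting child.** Assume the stopping day is uniform over study days 1 to 169. The targets for the four averaged visits are days 29, 57, 113 and 169 (SAP Table 12-1).

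- No ETT value: (28 + 56 + 112 + 168)/168 = 364/168 = 2.17 of 4 visits.
- ETT value 3 days after stopping: it fills an otherwise empty window only if stopping falls in days 19–29, 40–57, 82–113 or 138–169. Outside those ranges it lands before the Week 4 window opens, or in a window that already holds the scheduled value, which is nearer the target day. Visits recovered: (10 + 17 + 31 + 31)/168 = 89/168 = 0.53.
- Net loss with an ETT value: 2.17 − 0.53 = 1.64 visits.
- At the 10% ceiling: 54 × 0.10 × 1.64 = 8.9, about 9 of 54 × 4 = 216 active-arm visits.

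**3. Shift in the treatment difference, relative to keeping the off-drug data.** Further assumptions: the full effect of 1.0 is lost at once on stopping, and within-subject correlation is 0.6. Results are from a simulation with 400,000 per arm, averaged over two runs, SD 1.5, using a likelihood fit under missing at random with unstructured covariance and Day 15 included.

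| Active arm exiting | With ETT value | Share of 0.303 | No ETT value |
|---|---|---|---|
| 0 | 0 | 0% | 0 |
| 1 of 54 (1.85%) | 0.006 | 2% | 0.010 |
| 5% | 0.016 | 5% | 0.027 |
| 10% (ceiling) | 0.031 | 10% | 0.054 |

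The one-child row is scaled from the ceiling: 0.031 × 1.85/10 = 0.0057 and 0.054 × 1.85/10 = 0.010. A hand check of the no-ETT ceiling agrees: 0.10 × (2.17/4) × 1.0 = 0.054. With an ETT value the same formula gives 0.10 × (1.64/4) = 0.041. The simulated 0.031 is lower because the off-drug ETT value also informs the model's prediction of that child's later visits.

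**4. Sensitivity at the 10% ceiling, with an ETT value.** Correlation 0.4 gives 0.033 and 0.8 gives 0.029. Exits at the same rate in both arms give 0.031. If the ETT value still carries half the drug effect, the shift is 0.043.

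**The case against.** The best defence is that 9.7 is loose wording which the rest of the protocol corrects. Four sections agree against one clause in a short paragraph about dose modification, and 9.9 is the section devoted to removal of subjects. The protocol also speaks loosely of leaving the study elsewhere. Section 10.6 tells the investigator to consider discontinuing a noncompliant child from the study, while 9.9 treats noncompliance as a ground for stopping drug. Section 13.1.1.2 pairs a change in dose with discontinuation from the study. This makes a literal reading of 9.7 less likely, and it suggests that withdrawal from drug was intended. It does not remove the contradiction, because 9.7 is the section that a site would open when toxicity occurs.

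A reader might infer that the problem falls mainly on non-liver toxicities. Section 9.8.1 speaks only of stopping drug ("All subjects in whom treatment is discontinued for elevated transaminases" are to be monitored), whereas for rash 9.8.2 gives only an interruption rule: "Study drug dosing should be interrupted if a subject develops a generalized rash of Grade 3 or higher". The documents do not support that split. Section 9.7 covers any unacceptable toxicity and does not exempt liver events. Section 9.9 has all who discontinue drug return for assessments, so a child stopped for rash is kept in as plainly as one stopped for transaminases.

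A reader might also infer that some minimum share of the active arm must exit this way. No document gives such a rate. Protocol 5.1 reports only a low rate of treatment discontinuation in the studies of older subjects. An exit by this route needs both a toxicity stop and a site that reads 9.7 against four other sections, so none or one is plausible. The range has to start at zero.

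**Conclusion.** The inconsistency is real: 9.7 cannot be reconciled as written with 9.1.2, 9.1.4, 9.1.6 and 9.9. Its statistical effect is small. Over 0 to 10% of the active arm, the LCI2.5 difference moves in the drug's favour by 0 to about 0.03 with an ETT value and by up to about 0.05 without one, against a planned effect of 1.0. The 10% end is a ceiling, since it spends the plan's whole all-cause dropout allowance on this one route.

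The size rests on assumed exit rates, uniform stopping times, immediate loss of the full effect, a correlation of 0.6 and an ETT value about 3 days after stopping. It also takes as its reference an analysis that keeps off-drug values, which the visit plan in 9.1.4 implies. It would be wrong to read this as a threat to the primary conclusion. This is an optional correction, worth making because it concerns whether children with toxicity remain under observation.

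**What to change.** In Protocol 9.7, replace "individual subjects will be withdrawn from the study and dosing will cease" with wording to this effect: *subjects will be withdrawn from study drug treatment; scheduled visits continue per Section 9.1.4*. Dosing decisions stay as they are.

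The cost is one phrase in a protocol amendment or a clarification memo to sites. The visits are already planned under 9.1.4, so no procedure is added, and the SAP needs no change.
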